5.0 STUDY TREATMENT

5.1 Drug Regimen, Administration and Duration

- Both MMF and Myfortic© should be taken on an empty stomach, 1 hour before or 2 hours after food intake
- Entry / “Step 1” lead-in period:
 - Mycophenolate mofetil (MMF) 500 mg or Myfortic© 360 mg daily for one week as the “Step 1” lead-in phase
- Week 1 visit / “Step 2a” lead-in period:
 - Tolerability check
 - Start MMF 500 mg or Myfortic© 360 mg twice daily for 2 weeks as the “Step 2a” lead-in phase

Clinical Protocol

- Week 2 visit:
 - Tolerability check
 - Anti-proliferative testing
- Week 3 visit:
 - If week 2 test shows a desired anti-proliferative effect (>=80% reduction in T cell proliferation one-hour post dosing): continue study at MMF 500 mg or Myfortic© 360 mg twice daily for 22 months (“Step 3” enrollment)
 - If week 2 test does not show a desired anti-proliferative effect (<80% reduction in T cell proliferation one-hour post dosing): dose escalation to MMF 750 mg or Myfortic© 540 mg twice daily for 2 weeks (“Step 2b” lead-in phase)
- Week 4 visit (only if dose escalation to MMF 750 mg or Myfortic© 540 mg twice daily occurred at week 3 visit):
 - Tolerability check
 - Anti-proliferative testing
- Week 5 visit (if dose escalation to MMF 750 mg or Myfortic© 540 mg twice daily occurred at week 3)
 - If week 4 test shows a desired anti-proliferative effect (>=80% reduction in T cell proliferation one-hour post dosing): continue study at MMF 750 mg or Myfortic© 540 mg twice daily for 22 months (“Step 3” enrollment)
 - If week 4 test does not show a desired anti-proliferative effect (<80% reduction in T cell proliferation one-hour post dosing): discharge from study

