1.3 Study drug

Mycophenolate mofetil (MMF) is a prodrug of mycophenolic acid, which inhibits an enzyme required for proliferation of lymphocytes, including B and T cells. MMF is used to prevent organ rejection following lung, liver, heart and kidney organ transplantation. Moreover, MMF is commonly used as a steroid-sparing agent for autoimmune diseases.

MMF safety in HIV-infected patients has been established in over 300 HIV+ solid organ transplant recipients and other clinical settings.³⁹⁻⁵⁹ Fewer than 10% of treated participants developed nausea. Renal toxicity, cytopenia, opportunistic infections or decrease in peripheral CD4+ T cell counts were not noted.^{39-45,49} Of note, we will use 500mg twice daily in our study, which is lower than the 2-3g/day to prevent organ rejection. We will increase to 750 mg twice daily if an adequate anti-proliferative effect is not noted on a lower dose.

Myfortic[©] is an enteric coated version of the MMF which is associated with less nausea, vomiting and diarrhea. Myfortic[©] will be used for participants who have refractory nausea, vomiting and / or diarrhea on MMF, and who wish to remain in the study.

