If the information obtained at the eligibility visit indicates that a participant is eligible to participate in the study, we will ask them to come to the clinic for an entry visit. The purpose of this visit will be to enroll the participant in the study and obtain additional blood samples. We will ask all participants to take MMF for one week following this visit.

During this visit, we will do the following:

- 1) Draw 211 mL (43 teaspoons) of blood
- 2) Perform follow up urine pregnancy testing in female participants
- 3) Provide the study drug (MMF 500 mg daily) and instructions on how to use it.
- 4) Schedule follow-up visits
- 5) Answer any questions
- 6) Focused physical exam as needed

One-Week Visit (approximately 30 minutes) / Step 2a Lead-in

Six days after enrolling in the study, we will ask participants to make a follow-up visit to discuss tolerability of the drug. Participants will be seen in the morning of day 7. If they are tolerating the dose, then their dose will be increased to MMF 500 mg twice daily.

At this visit, we will:

- 1) Draw a combined total of 10.5 mL of blood (about 2 teaspoons).

Clinical Protocol

- 2) Ask the participant how they are tolerating the study medication
- 3) Answer any questions
- 4) Focused physical exam as needed

Two-Week Visit (approximately 30 minutes)

Thirteen days after enrolling in the study, we will ask participants to make a follow-up visit to measure anti-proliferative effect at trough and peak MMF levels. Participants will be seen in the morning of day 14, approximately 12 hours after the last evening MMF dose. We will draw a small blood sample, then administer the morning MMF dose, ask the participant to wait for 60 minutes, and then take another small sample. We will use the first sample to assess the anti-proliferative effect at trough MMF levels, and the second sample to assess the anti-proliferative effect at peak MMF levels. At this visit, we will:

- 5) Draw a combined total of 46.5 mL of blood (about 9 teaspoons) on 2 occasions separated by 1 hour.
- 6) Ask the participant how they are tolerating the study medication
- 7) Answer any questions
- 8) Focused physical exam as needed

Three-Week Visit (approximately 30 minutes)

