The purpose of this visit is to determine how the participant is responding to the study drug. Based on the results of the peak MMF time point studies done in the lab, we will determine whether the participant is eligible to continue participating in the study at the current dose for 22 months (Step 3 / Enrollment) or might require a dose escalation (Step 2b / lead-in).

If a participant does not have the desired anti-proliferative effect to MMF 500 mg twice daily at the two-week visit, we will administer MMF 750 mg po twice daily (Step 2b / lead-in): this will occur at the three-week visit because it takes approximately one week for the anti-proliferative assay to be performed.

No blood will be drawn at the three-week visit.

Four-Week Visit (approximately 30 minutes)

For participants on 500 mg bid and those who required dose escalation to 750 mg bid, we will recheck for an anti-proliferative effect at a week 4 visit. Participants will be seen in the morning, approximately 12 hours after the last evening MMF dose. We will draw a small blood sample, then administer the morning MMF dose, ask the participant to wait for 60 minutes, and then take another small sample. We will use the first sample to assess the anti-proliferative effect at trough MMF levels, and the second sample to assess the anti-proliferative effect at peak MMF levels. At this visit, we will:

- 1) Draw a combined total of 157.5 mL of blood (about 11 teaspoons) on 2 occasions separated by 1 hour.
- 2) Ask the participant how they are tolerating the study medication

Clinical Protocol

- 3) Answer any questions
- 4) Focused physical exam as needed

Five-Week Visit (approximately 30 minutes): only for participants receiving 750 mg po bid

The purpose of this visit is to determine how participants who required escalation to 750 mg bid are responding to the study drug. Based on the results of the peak MMF time point studies done in the lab on the week 4 visit, we will determine whether the participant is eligible to continue participating in the study at the current dose for 22 months (Step 3 / Enrollment).

If participants do not have the desired anti-proliferative effect to MMF 750 mg twice daily, they will be discharged from the study at the week 5 visit.

No blood will be drawn at the week 5 visit.

Treatment Modification

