If a participant develops nausea or diarrhea anytime during the first week on MMF 500 mg daily, we will offer the participant a change from MMF 500 mg daily to Myfortic© 360 mg daily. Myfortic© is an enteric coated version of MMF which is associated with less nausea and diarrhea in certain patients. If the participant tolerates the first week of Myfortic© 360 mg daily, then we will switch to Myfortic© 360 mg twice daily during the second week. If this is tolerated, then we will test for an anti-proliferative effect per protocol.

In the case of refractory nausea or diarrhea after week one, participants will be offered a change from MMF 500 mg twice daily to Myfortic© 360 mg twice daily. If a study participant is on MMF 750 mg twice daily, then we will switch to Myfortic© 540 mg twice daily. Participants will always have the option of withdrawing their participation from the trial rather than switching to Myfortic©.

Follow-up Visits (approximately 30 minutes)

Over the course of the study, we will ask participants to come in 19 more times (**Table 2**). Starting at entry, for the first month, we will ask them to come in weekly, then every other week for two months, then every month for the rest of the first 12 months, then at month 15, month 18½, and a final visit at 22 months. The purpose of these visits is to obtain samples to measure how the drug is affecting the HIV reservoir and to check safety labs.

We will check to see if the amount of HIV infected cells is decreasing after one year and after two years. If not, then we will ask the participant to stop participating in the study as we wish to see an effect of the drug at that point in time.

Influenza vaccination will occur at one follow-up visit unless study participants have already received this vaccine in the community.

During these visits, we will do the following:

Clinical Protocol

- 1) Draw between 6.5 and 255 mL of blood depending on visit (**Table 2**).
- 2) Draw 2 sets of blood separated by an hour to obtain peak and trough drug levels (weeks, 12, 24, 48, 74 & 88).
- 3) Perform follow up urine pregnancy testing in female participants (point-of-care-test in the clinic)
- 4) Ask how the participant is tolerating the study medication
- 5) Answer any questions
- 6) Discuss continuation in the study
- 7) Perform a focused physical exam as needed

Optional Rectal Biopsy Visit (up to 2 hours)

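### The 80% anti-proliferation test is read one hour after dosing for both plain MMF and enteric-coated Myfortic, so it may read a Myfortic user below true peak and trigger an unneeded escalation or, after a second low reading, discharge

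*Combined protocol and SAP*

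**What the plan says.** Section 5.1 sets one criterion for both products: at least an 80% fall in T cell proliferation one hour after the dose. At week 2 a participant who misses it follows the branch "<80% reduction in T cell proliferation one-hour post dosing): dose escalation to MMF 750 mg or Myfortic" 540 mg twice daily. At week 4, after that escalation, a second miss leads to "<80% reduction in T cell proliferation one-hour post dosing): discharge from study". A pass fixes the dose for 22 months.

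Section 6.1 describes a single test procedure. A trough sample is drawn about 12 hours after the evening dose, the morning dose is given, and staff then "ask the participant to wait for 60 minutes, and then take another small sample". The dose decision is made "Based on the results of the peak MMF time point studies done in the lab"; the trough sample plays no part in it. The later paired visits (weeks 12, 24, 48, 74 and 88) use the same spacing: "Draw 2 sets of blood separated by an hour to obtain peak and trough drug levels".

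Section 1.3 says that Myfortic "is an enteric coated version of the MMF which is associated with less nausea, vomiting and diarrhea". Under Treatment Modification in section 6.1, a participant with nausea or diarrhea in week 1 may change to Myfortic, and then: "If this is tolerated, then we will test for an anti-proliferative effect per protocol". No section gives a different sampling time for Myfortic, a release lag or time to peak for either product, or a reason why one hour is the peak for the coated tablet.

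**The concern.** An enteric coat is there to delay release. A sampling time that suits plain MMF may therefore fall before the Myfortic peak. The same 80% threshold would then be a stricter requirement for Myfortic users, because they would be assessed on a partly risen level.

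The reading sets the dose for 22 months. A falsely low one gives a person who already had gastrointestinal intolerance 50% more immunosuppressant each day (2 × 360 = 720 mg to 2 × 540 = 1080 mg). A second falsely low one removes that person, who is replaced under section 6.7 as lacking an anti-proliferative effect. In a trial of five, that would also move the tolerability result (a secondary objective) toward people who tolerated plain MMF.

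**Working it through.** The plan gives no figure to reproduce. The question is how far a 60-minute sample can fall short of peak before the decision changes.

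**Inputs from the documents.** Threshold 80%, 60-minute draw, and doses of 360 and 540 mg twice daily (sections 5.1 and 6.1). Trough about 12 hours after the previous dose (section 6.1). In a cited low-dose MMF study, more than 60% inhibition at 12 hours in 6 of 9 subjects (section 1.2). "Fewer than 10% of treated participants developed nausea" (section 1.3). One of 5 expected to fail the test (section 9.0). Eight-week blood limit 450 mL (Table 2, section 9.0).

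**Assumptions not in the documents.** Inhibition I = kx/(1 + kx), where x is the drug level as a fraction of true peak and k = I/(1 − I) at true peak. Trough r is 5%, 10%, 20% or 40% of peak. A share f of the trough-to-peak rise is reached by 60 minutes. The level is proportional to dose.

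**Step 1: the reading.** At 60 minutes x = r + f(1 − r). The test is passed when kx ≥ 4, since 4/(1 + 4) = 80%. For true-peak inhibition of 90%, k = 0.90/0.10 = 9. Example: r = 0.20 and f = 0 give kx = 1.8 and a reading of 1.8/2.8 = 64.3%.

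| Trough r | f = 0 | f = 0.25 | f = 0.5 | f = 1 | f needed to pass |
|---|---|---|---|---|---|
| 5% | 31.0% | 72.1% | 82.5% | 90% | 0.415 |
| 10% | 47.4% | 74.5% | 83.2% | 90% | 0.383 |
| 20% | 64.3% | 78.3% | 84.4% | 90% | 0.306 |
| 40% | 78.3% | 83.2% | 86.3% | 90% | 0.074 |

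The last column is (4/k − r)/(1 − r).

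**Step 2: after escalation.** At 540 mg, k = 9 × 1.5 = 13.5 (true peak 93.1%). With f = 0 the readings are 40.3%, 57.4%, 73.0% and 84.4%. The share needed to pass is 0.259, 0.218, 0.120 and none.

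**Step 3: the standard actually applied.** The true-peak inhibition needed to read 80% at one hour is (4/x)/(1 + 4/x). It is 80% at f = 1, 85–88% at f = 0.5, 88–93% at f = 0.25 and 91–99% at f = 0.

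**Step 4: expressed as a lag.** Take a one-compartment model at steady state with 12-hourly dosing, absorption rate ka of 2 or 4 per hour and half-life of 3, 4 or 6 hours (all assumed). The level is proportional to exp(−ke·t)/(1 − exp(−12ke)) − exp(−ka·t)/(1 − exp(−12ka)), with t the hours since release and ke = ln 2/half-life. With a 45-minute lag, a 90% responder reads 83–88% and passes, while someone exactly at 80% reads 69–76%. With lags of 60, 90 or 120 minutes the 90% responder reads 41–76%.

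**Step 5: the trough evidence in section 1.2.** Inhibition above 60% at 12 hours means kx > 1.5, so with k = 9 the trough exceeds 1.5/9 = 16.7% of peak. For responders of that kind the 5% and 10% rows do not apply. Even so, with nothing released by 60 minutes, a 60% trough reading (kx = 1.5) is below 80%, and at 540 mg it becomes 2.25/3.25 = 69%.

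**Step 6: how many.** If 1 in 5 fails, about 5/0.8 ≈ 6 people enter the lead-in. If each is on Myfortic at the test with probability p, the chance of at least one is 1 − (1 − p)^6: 26% at p = 5%, 47% at 10% and 74% at 20%. The expected number, 6p, is 0.3, 0.6 and 1.2.

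**The case against.** The strongest reply is that the decisive quantity is not in the documents. A reader might infer that the 60-minute sample is drawn before any Myfortic is released. Nothing in the protocol supports that: it mentions the coating only in connection with gastrointestinal tolerability. The calculation above also passes a 90% responder at a 45-minute lag. Participants are on repeated twice-daily dosing by then, so at most the morning dose could be unreleased, and carry-over counts toward the reading. The 12-hour inhibition figure in section 1.2 comes from plain MMF in another study, but it is the only anchor available and makes the lowest readings less likely for responders. All of this stands, and it makes the concern conditional.

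A reader might also infer that one low reading ends participation. It does not: it leads to a planned higher dose with a tolerability check, and discharge needs a second failure. The second test has the same timing, however, so its error would tend to repeat the first.

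Nor does a false failure use up an allowance of 1 in 5. Section 9.0 gives that as an estimate and continues screening until five are enrolled, and section 6.7 replaces people who fail the test.

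The frequency figures are soft. The section 1.3 rate is an upper bound for nausea and is not specific to the lead-in weeks. Section 1.3 reserves Myfortic for refractory symptoms, ondansetron is available, and a participant may withdraw rather than switch. The 20% value is an assumption that allows for diarrhea.

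**Conclusion.** The concern holds in conditional form. The plan applies one threshold at one sampling time to an uncoated and an enteric-coated product, calls the sample a peak for both, and gives no justification for the second. Depending on lag and trough, an adequately inhibited Myfortic user could be escalated after one low reading, and discharged and replaced only after a second.

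For a participant with 90% true-peak inhibition, the error does not change the decision once about 42% of the rise is reached by 60 minutes, or about 31% if trough is 20% of peak. If nothing is reached, that participant is escalated at all four assumed troughs and, after escalation, discharged at three of them. At the two troughs compatible with the section 1.2 figure, discharge follows at one. These results rest on the assumed effect curve, trough range and dose proportionality. The documents cannot show which case applies.

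Few people are likely to be affected: only those on Myfortic by the week 2 or week 4 test. With five participants and a dose fixed for 22 months, the timing should still be set or justified before the test is used.

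**What to change.** Keep the 80% threshold, and keep the 60-minute draw for plain MMF. In sections 5.1 and 6.1, state that for anyone on Myfortic at the week 2 or week 4 test, and at the later paired visits, the post-dose sample is taken at the Myfortic time to peak in the product information, in place of the 60-minute sample. When a reading falls below 80%, review the paired trough and post-dose drug levels, which Table 2 already plans at week 2, before acting on it.

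Move the draw rather than add one. The total in Table 2 at the week 4 peak sample is 23 + 211 + 10.5 + 31 + 15.5 + 142 + 15.5 = 448.5 mL, and one more 15.5 mL sample would give 464 mL against the 450 mL limit. For the same reason, do not add a rule that holds the dose and repeats the test. A true non-responder escalated later would need a further paired test of 2 × 15.5 = 31 mL, which gives 479.5 mL, or 456.5 mL once the 23 mL eligibility draw has left the eight-week window.

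The change needs no extra blood and no extra assay. Its cost is a longer wait for Myfortic users at those visits. A fixed later time can still miss a late peak, and the review of drug levels only partly guards against that.

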5.2 Drug Formulation

MMF tablets, 250 mg, 500 mg
Myfortic© tablets, 180 mg, 360mg

5.3 Drug Supply

- Drugs will be procured locally in Seattle and stored by the AIDS Clinical Trial Unit pharmacy at Harborview Medical Center. Only drugs approved by the US Food and Drug Administration (FDA) will be used.

6.0 PARTICIPANT MANAGEMENT

6.1 Procedures

Participants in this study will take 500 mg MMF once per day for one week as a lead in to limit drug-related side effects. Provided they are tolerating the drug at lower dose, they will then initiate 500 mg MMF twice a day for 22 months in addition to their regular anti-HIV treatment. MMF will be switched to Myfortic© in the event of poorly tolerated nausea, vomiting or diarrhea and participant agreement to remain in the study. As described above, dose escalation to 750 mg MMF twice daily is possible in the event of an inadequate anti-proliferative effect. Participants will visit the clinic and provide samples (blood and optional rectal biopsies) several times during the course of the study. If feeling nausea or vomiting, participants will be offered ondansetron 4mg oral tablets. The specific procedures for the study visits are outlined below.

Eligibility Visit (approximately 2 hours)

Clinical Protocol

During this visit, we will do the following:

- 1) Provide participants with general information about the 2 West Clinic
- 2) Ask participants to sign the Study Consent Form, the Release of Medical Information Form, and HIPAA Authorization Form
- 3) Document that participants have HIV by medical records and also determine if participants have a medical condition that would preclude them from entering the study. In the event that documentation is unavailable, we will ask participants to allow us to do these tests after counseling and obtaining their verbal consent
- 4) Take a medical and medication history
- 5) Assess substance use history, including alcohol, and sexual risk behavior
- 6) Perform a general clinical exam (including vital signs: weight, height, blood pressure, pulse and temperature)
- 7) Obtain a urine specimen for pregnancy testing in female participants
- 8) Draw about 5 teaspoons of blood for routine blood tests (blood cell counts and signs of anemia, kidney or liver dysfunction)
- 9) Perform blood testing for hepatitis B and C if results are not already available from within 12 months prior to eligibility visit.

Entry Visit (approximately 1 hour) / Step 1 Lead-in

If the information obtained at the eligibility visit indicates that a participant is eligible to participate in the study, we will ask them to come to the clinic for an entry visit. The purpose of this visit will be to enroll the participant in the study and obtain additional blood samples. We will ask all participants to take MMF for one week following this visit.

During this visit, we will do the following:

- 1) Draw 211 mL (43 teaspoons) of blood
- 2) Perform follow up urine pregnancy testing in female participants
- 3) Provide the study drug (MMF 500 mg daily) and instructions on how to use it.
- 4) Schedule follow-up visits
- 5) Answer any questions
- 6) Focused physical exam as needed

One-Week Visit (approximately 30 minutes) / Step 2a Lead-in

Six days after enrolling in the study, we will ask participants to make a follow-up visit to discuss tolerability of the drug. Participants will be seen in the morning of day 7. If they are tolerating the dose, then their dose will be increased to MMF 500 mg twice daily.

At this visit, we will:

- 1) Draw a combined total of 10.5 mL of blood (about 2 teaspoons).

Clinical Protocol

- 2) Ask the participant how they are tolerating the study medication
- 3) Answer any questions
- 4) Focused physical exam as needed

Two-Week Visit (approximately 30 minutes)

Thirteen days after enrolling in the study, we will ask participants to make a follow-up visit to measure anti-proliferative effect at trough and peak MMF levels. Participants will be seen in the morning of day 14, approximately 12 hours after the last evening MMF dose. We will draw a small blood sample, then administer the morning MMF dose, ask the participant to wait for 60 minutes, and then take another small sample. We will use the first sample to assess the anti-proliferative effect at trough MMF levels, and the second sample to assess the anti-proliferative effect at peak MMF levels. At this visit, we will:

- 5) Draw a combined total of 46.5 mL of blood (about 9 teaspoons) on 2 occasions separated by 1 hour.
- 6) Ask the participant how they are tolerating the study medication
- 7) Answer any questions
- 8) Focused physical exam as needed

Three-Week Visit (approximately 30 minutes)

The purpose of this visit is to determine how the participant is responding to the study drug. Based on the results of the peak MMF time point studies done in the lab, we will determine whether the participant is eligible to continue participating in the study at the current dose for 22 months (Step 3 / Enrollment) or might require a dose escalation (Step 2b / lead-in).

If a participant does not have the desired anti-proliferative effect to MMF 500 mg twice daily at the two-week visit, we will administer MMF 750 mg po twice daily (Step 2b / lead-in): this will occur at the three-week visit because it takes approximately one week for the anti-proliferative assay to be performed.

No blood will be drawn at the three-week visit.

Four-Week Visit (approximately 30 minutes)

For participants on 500 mg bid and those who required dose escalation to 750 mg bid, we will recheck for an anti-proliferative effect at a week 4 visit. Participants will be seen in the morning, approximately 12 hours after the last evening MMF dose. We will draw a small blood sample, then administer the morning MMF dose, ask the participant to wait for 60 minutes, and then take another small sample. We will use the first sample to assess the anti-proliferative effect at trough MMF levels, and the second sample to assess the anti-proliferative effect at peak MMF levels. At this visit, we will:

- 1) Draw a combined total of 157.5 mL of blood (about 11 teaspoons) on 2 occasions separated by 1 hour.
- 2) Ask the participant how they are tolerating the study medication

Clinical Protocol

- 3) Answer any questions
- 4) Focused physical exam as needed

Five-Week Visit (approximately 30 minutes): only for participants receiving 750 mg po bid

The purpose of this visit is to determine how participants who required escalation to 750 mg bid are responding to the study drug. Based on the results of the peak MMF time point studies done in the lab on the week 4 visit, we will determine whether the participant is eligible to continue participating in the study at the current dose for 22 months (Step 3 / Enrollment).

If participants do not have the desired anti-proliferative effect to MMF 750 mg twice daily, they will be discharged from the study at the week 5 visit.

No blood will be drawn at the week 5 visit.

Treatment Modification

If a participant develops nausea or diarrhea anytime during the first week on MMF 500 mg daily, we will offer the participant a change from MMF 500 mg daily to Myfortic© 360 mg daily. Myfortic© is an enteric coated version of MMF which is associated with less nausea and diarrhea in certain patients. If the participant tolerates the first week of Myfortic© 360 mg daily, then we will switch to Myfortic© 360 mg twice daily during the second week. If this is tolerated, then we will test for an anti-proliferative effect per protocol.

In the case of refractory nausea or diarrhea after week one, participants will be offered a change from MMF 500 mg twice daily to Myfortic© 360 mg twice daily. If a study participant is on MMF 750 mg twice daily, then we will switch to Myfortic© 540 mg twice daily. Participants will always have the option of withdrawing their participation from the trial rather than switching to Myfortic©.

Follow-up Visits (approximately 30 minutes)

Over the course of the study, we will ask participants to come in 19 more times (**Table 2**). Starting at entry, for the first month, we will ask them to come in weekly, then every other week for two months, then every month for the rest of the first 12 months, then at month 15, month 18½, and a final visit at 22 months. The purpose of these visits is to obtain samples to measure how the drug is affecting the HIV reservoir and to check safety labs.

We will check to see if the amount of HIV infected cells is decreasing after one year and after two years. If not, then we will ask the participant to stop participating in the study as we wish to see an effect of the drug at that point in time.

Influenza vaccination will occur at one follow-up visit unless study participants have already received this vaccine in the community.

During these visits, we will do the following:

Clinical Protocol

- 1) Draw between 6.5 and 255 mL of blood depending on visit (**Table 2**).
- 2) Draw 2 sets of blood separated by an hour to obtain peak and trough drug levels (weeks, 12, 24, 48, 74 & 88).
- 3) Perform follow up urine pregnancy testing in female participants (point-of-care-test in the clinic)
- 4) Ask how the participant is tolerating the study medication
- 5) Answer any questions
- 6) Discuss continuation in the study
- 7) Perform a focused physical exam as needed

Optional Rectal Biopsy Visit (up to 2 hours)

We will give all participants the option of providing rectal biopsy samples once before starting the study medication, once at 12 months, and once at 22 months. Volunteers will be asked to have a bowel movement at home or in the clinic before the procedure. No other preparation is required. An anoscope will be inserted, and small amounts of rectal tissue from up to six locations will be biopsied. Medications e.g Lidocaine cream may be offered to participants to provide comfort prior to the rectal biopsy procedure. To reduce the risks of the procedure, we will ask the participants not to have anal sex for 5 days afterwards. Before undergoing the first procedure, participants will have their prothrombin time (PT), partial thromboplastin time (PTT) and platelet counts evaluated.

Storage of Data and Leftover Samples for Use in Future Research

Participants will be asked for permission to keep data and any remaining samples for possible use in future research studies. Residual samples will be stored indefinitely at the University of WA and/or Fred Hutch. Before conducting additional research unrelated to the original research questions, the UW HSD will review the request.

Specimens may be shared with other investigators at the UW, Fred Hutch or other institutions. The samples may not be sold or used directly for production of any commercial product. Tests may include genetic research. Each sample will be encoded (labeled) *only* with a barcode and a unique tracking number to protect participant's confidentiality.

There are no benefits to participants in the collection, storage, and subsequent research use of samples. Reports about future research done with a participant's samples will not be kept in their health records. A participant's decision can change at any time up to the point the samples are released for research use by notifying the study doctors in writing. However, if a participant consents to future use and some of their sample has already been used for research purposes, the information from that research may still be used. Participants may also withdraw their permission by asking the researchers to anonymize their samples.

